## 7.0 STOPPING RULES AND DISCONTINUATION CRITERIA

## 7.1 Management of individual patients who experience clinically significant toxicity

In the event of a patient experiencing significant toxicity the PI and the Sponsor Medical Director will examine the circumstances. If this is not possible the Principal PI or any other physician having direct responsibility for the patient's treatment may take appropriate action. The patient will be withdrawn from the trial and offered alternative treatment in the event of any of the following:

- An adverse event graded serious or severe which in the opinion of the TSC is probably or definitely related to administration of the trial drug and which would prejudice the patient's well-being if it was to continue or recur.
- Any other reason for which, in the opinion of the Principal PI or the TSC, it would not be in the best interests of the patient to remain in the trial.
- At the request of the patient for any reason.

## 7.2 Toxicity occurring in two or more patients

In the event of the same or a similar severe adverse event occurring in two or more patients in the trial and which, in the opinion of the PI, is possibly, probably or definitely related to administration of Coversin consideration will be given to halting the trial. A serious adverse event (SAE) occurring in two or more patients which is probably or definitely drug related is

an absolute indication to terminate the trial. Adverse events which are not SAEs but which appear to affect more than one patient will be assessed for their severity, threat to the patients' health and drug relationship and a decision on whether to halt the trial or allow it to continue while keeping the situation under review will be made by the PI and the Sponsor Medical Director.

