## **Protocol synopsis**

	Exclusion Criteria:		
	• Pregnancy (females)		
	• Known allergy to ticks or severe reaction to arthropod venom (e.g. bee or wasp venom)		
	• Failure to satisfy the PI of fitness to participate for any other reason		
Treatment Regimen:	Single ablating dose of 0.57mg/kg per subject followed by daily maintenance doses. The initial maintenance dose will be 25% of the ablating dose. If this is insufficient to maintain complement activity at $\leq 10\%$ of baseline (pre-treatment) level after 5 days of treatment the daily maintenance dose will be increased by doubling until that level of inhibition is achieved. In the event of 100% inhibition being achieved the dose may be titrated downwards at the PI's discretion until a satisfactory clinical result is obtained. If at any point in treatment complement activity (CH50) is 50% of baseline or more a further ablating dose of 0.57mg/kg should be given. An increased daily maintenance dose may be required in the event of intercurrent infection or illness. CH50 level should be checked in the event of deteriorating clinical response manifested by rising serum LDH.		
Duration of Treatment:	Patients will undergo an initial period of 6 months treatment according to this protocol. At the expiry of this period, and on the recommendation of the PI, patients will have the option of remaining on long-term Coversin therapy and will enter the long term follow-up study.		
Endpoints:	Efficacy Endpoints:		
	Primary: Reduction in serum LDH from day 0 – Day 28		
	Secondary: Hb, haptoglobin, Fatigue (FACIT), Quality of Life (EORTC QL-C30), PNH RBC clone size, Transfusion requirement		
	Safety Endpoints:		
	Adverse events, ECG, Laboratory results, Vital signs.		
Statistical Methods:	Descriptive statistics		

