## 5.0 SUBJECT WITHDRAWAL CRITERIA

Subjects may be withdrawn from the trial in the following circumstances:

• An adverse event graded serious or severe which in the opinion of the PI is possibly, probably or definitely related to administration of the trial drug.

- Any other reason for which, in the opinion of the PI it would not be in the best interests of the subject to remain in the trial.
- At the request of the subject for any reason.
- Non-compliance or behaviour not compatible with the proper conduct of the trial.

Appropriate clinical and serological data will be entered in the CRFs. In addition the Subject Withdrawal page of the CRFs will be completed. All data that would normally have been entered on the final day of dosing will be collected and entered together with such additional data as the PI considers clinically necessary to ensure the subject's safety or to elucidate the nature of the AE (e.g. special tests, X Rays, scans, photographs etc.)

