- If LDH is decreasing and if CH50 is between 50 and 10% of baseline, the maintenance dose may be increased according to the schedule of increments of maintenance dose shown below.
- If LDH is not reducing and CH50 is >50% of baseline the patient must either be discontinued from the trial and switched to alternative therapy or must be readmitted to hospital for dose stabilisation following another ablating dose (0.57mg/kg) of Coversin. In either case the findings and course of action must be discussed by a Trial Steering Committee comprised of, at minimum, the PI, and the Medical Director of the Sponsor company.

The schedule of increments for the maintenance dose is as follows:

Ablating dose	First maintenance	Second mainte-	Third mainte-
	dose level	nance dose level	nance dose level
0.57 mg/kg	0.14 mg/kg	0.29 mg/kg	0.57 mg/kg

Within each patient the first incremented maintenance dose should be given at 24 hour intervals for at least 4 days until steady state is reached and at that point a CH50 assay should be performed. If the CH50 is not  $\leq 10\%$  of baseline (adjusted to 100%) then the next incremental dose (Second maintenance dose level should be given for at least another 4 days before switching to the Third maintenance dose level. If at any

stage the CH50 is >50% of baseline another ablating dose should be given before using the next incremental dose.

[figure not shown]
Blood samples and timing is shown in Appendix 1. Samples for CH50, antibodies and drug level should be processed as shown in Section 20 and sent to the Akari Therapeutics Plc complement laboratory for assaying. All other laboratory tests should be done locally in the PI's hospital laboratory.

If an ablating dose is repeated , PK/PD and other assessment will be performed as indicated in Appendix 1 at 1hr, day 2 and day 5.

At increments of the maintenance dose PK and PD and other assessments are repeated at day 5 as indicated in Appendix 1.

Extra samples for PK/PD may be taken at the discretion of the investigators during illness or infection.

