#### Flow chart: Schedule of Procedures and Visits

The trial will continue for 6 months or until it has been decided by the PI in consultation with the Sponsor Company that further Coversin treatment is futile or not in the patient's best interests. If the patient is satisfactorily controlled and wishes to continue on Coversin he/she will be permitted to enter the long-term follow-up study. Drug will, if necessary, be supplied free of charge by the Sponsor until it is approved for this indication and reimbursed through the normal channels.

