#### 12.6 Adverse event reporting

All Serious or Severe adverse events, whether or not considered to be drug related, will be reported immediately to the PI and the Sponsor who will be responsible for reporting it/them to the regulatory authority (MHRA) and the Ethics Committee within 24 hours of learning of its occurrence.. They will be recorded on the appropriate CRF with a description of the outcome. Non-serious moderate or mild adverse events will be recorded in the CRFs but need not be reported to the Sponsor at the time unless there are unusual circumstances (e.g. the adverse event was of a completely unexpected nature); they should be reported to the Safety Monitoring Committee within sufficient time for decisions regarding dose escalation to be made.

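### Every halting rule in section 7.2 needs events in more than one patient, so one drug-related SAE requires no decision on enrolment and no hold on the next first dose

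*Combined protocol and SAP*

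**What the plan says.** The synopsis and sections 1.6 and 13.2 set enrolment at one to six patients. The synopsis lists one centre.

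Section 7.2 contains three trial-level provisions:
- The same or a similar severe adverse event, at least possibly related, in two or more patients: halting is considered.
- "A serious adverse event (SAE) occurring in two or more patients which is probably or definitely drug related": the trial must be terminated.
- Non-serious events that appear to affect more than one patient: "a decision on whether to halt the trial or allow it to continue while keeping the situation under review will be made". Those who decide are the PI and the Sponsor Medical Director.

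For one affected patient, section 7.1 applies: "In the event of a patient experiencing significant toxicity the PI and the Sponsor Medical Director will examine the circumstances". If that is not possible, a responsible physician may act. The patient is withdrawn if, among other grounds, the Trial Steering Committee (TSC) considers a serious or severe event probably or definitely related and harmful to that patient if it continued or recurred. Section 6.0 describes "a Trial Steering Committee comprised of, at minimum, the PI, and the Medical Director of the Sponsor company".

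Section 12.6 sends every serious or severe event to the PI and sponsor, and on to the regulator and Ethics Committee within 24 hours. Section 6.2 sets the later fixed maintenance dose from the first patient's results.

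**The concern.** Safety is the primary objective, and section 1.3 describes clinical experience with Coversin as limited. Suppose one of the first patients has a related fatal or life-threatening event. Followed to the letter, the protocol lets the next eligible patient receive a first dose with no recorded decision that the trial should go on.

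Two features make this more than a gap in detail. First, the rules are uneven: non-serious events in more than one patient force a halt-or-continue decision, and one related death does not. Second, the open questions after a first event concern later patients:
- **Prophylaxis.** Meningococcal infection is the recognised hazard of C5 blockade (sections 1.3 and 10.0), and sections 3.0 and 10.0 allow either continuous or on-demand antibiotics. One such infection would raise the question of whether the next patient should have the on-demand option.
- **Dose.** After the switch to lyophilised product, section 6.2 gives later patients a fixed 60 mg ablating dose. At the 50 kg lower weight limit that is 60/50 = 1.2 mg/kg, about 2.1 times the 0.57 mg/kg of the weight-based regimen. At 100 kg it is 0.6 mg/kg.

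**Working it through.** **Does another section fill the gap?** These are the provisions that could apply after one related SAE, and what each requires:
- Section 5.0: "Subjects may be withdrawn from the trial in the following circumstances". The outcome is withdrawal of that subject.
- Section 7.1: joint examination and a TSC view on causality. The stated outcome is withdrawal of that patient.
- Section 6.0, flow chart text: treatment runs for 6 months or until it is "decided by the PI in consultation with the Sponsor Company that further Coversin treatment is futile or not in the patient's best interests". The ground is futility or one patient's interest.
- Section 6.0, TSC: its stated task there is one patient's failure to respond to dosing.
- Section 6.2: a dose decision after the first patient, aimed at complement inhibition and not framed as a safety review.
- Section 12.6, Safety Monitoring Committee: "they should be reported to the Safety Monitoring Committee within sufficient time for decisions regarding dose escalation to be made". The events meant are non-serious mild or moderate ones.
- Section 12, reporting: who is told and when, with no consequence for enrolment.
- Synopsis, exclusion criteria: "Failure to satisfy the PI of fitness to participate for any other reason". This is a judgement about the entrant.

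None requires an enrolment decision or a hold. A DSMB appears only in the abbreviation list. Appendix 1 was not in the text I read; the protocol cites it for visits and sampling.

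**How often would the two-patient SAE rule stay silent?** The protocol gives no operating characteristics, so there is no figure to reproduce. The following is an illustration.

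Inputs: n = 6 patients (section 13.2), assumed independent, each with probability p of a related SAE. The protocol gives no rate for Coversin. The lowest value is the 2 of 96 meningococcal cases on eculizumab in section 1.3, which is another drug and one event type. The values 10% to 50% are assumptions.

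Formulas:
- P(at least one) = 1 − (1−p)^6
- P(exactly one) = 6p(1−p)^5
- P(two or more) = P(at least one) − P(exactly one)
- P(silent, given at least one) = P(exactly one) / P(at least one)

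Example at p = 0.10: 1 − 0.9^6 = 0.4686; 6 × 0.1 × 0.9^5 = 0.3543; 0.3543/0.4686 = 0.756.

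| p | At least one | Exactly one | Rule fires | Silent, given at least one |
|---|---|---|---|---|
| 2/96 | 11.9% | 11.3% | 0.6% | 94.8% |
| 10% | 46.9% | 35.4% | 11.4% | 75.6% |
| 20% | 73.8% | 39.3% | 34.5% | 53.3% |
| 30% | 88.2% | 30.3% | 58.0% | 34.3% |
| 50% | 98.4% | 9.4% | 89.1% | 9.5% |

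With three patients enrolled, the last column is 89.7%, 78.7%, 67.1% and 42.9% at 10%, 20%, 30% and 50%. With one patient the rule can never fire, but there is then no later patient to protect.

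The table counts any related SAE in two patients. If the rule is read as needing the same SAE twice, it fires less often.

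**How often would a first-event hold touch a later patient?** Let q be the rate of SAEs rated possibly related or related. It may exceed p, because the category is wider. If patients are dosed one after another and each outcome is known before the next first dose, the probability is 1 − (1−q)^(n−1). For n = 6 and q = 10%, 20%, 30%: 1 − 0.9^5 = 41%, 1 − 0.8^5 = 67%, 1 − 0.7^5 = 83%. For n = 3: 19%, 36%, 51%. An actual delay arises only if a patient presents during the review.

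**The case against.** The strongest reply is that the right people already act. The minimum TSC is the PI and the Sponsor Medical Director, who examine the event and judge its causality under 7.1. The PI also decides who is fit to enter, and the sponsor supplies the drug. Outside bodies hear of a serious event within 24 hours, whereas mild or moderate non-serious events need not reach the sponsor at the time. Nothing forbids a discretionary halt. On this view the change adds only a pause and a note, in a study of at most six patients, and alters no estimate or analysis.

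Most of that is correct, and it limits the point. A reader might infer that a single related death goes unreviewed, or that the trial must carry on after it. The documents do not support either reading. What stands is narrower: the examination, the causality view, the reporting and the fitness judgement each have some other stated purpose, and none has to end in a decision about the next patient.

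A reader might also infer from the lower rates that the two-patient rule generally fails. It does not. At an assumed 50% rate it fires in 89% of six-patient trials. The gap is widest at low to moderate rates.

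**Conclusion.** The point holds in this limited form. After one related SAE the protocol requires review and reporting for the affected patient, but no decision on continued enrolment and no hold on the next first dose. It does require a halt-or-continue decision for non-serious events in more than one patient. That conclusion rests on the text and needs no assumed rate.

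Its practical size depends on assumptions: six patients enrolled, independence, and SAE rates the protocol does not give. Across 2% to 50%, the share of trials with a related SAE in which the mandatory rule never fires runs from about 95% down to about 10%. In some of those trials the affected patient would be the last one enrolled, so no later patient would be exposed.

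The one-centre description rests on the synopsis. Sections 14, 15 and 17 speak of hospitals in the plural. With more than one site, the PI's own knowledge of an event would be a weaker safeguard.

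This is a safety-governance change worth making. It does not affect the efficacy analysis.

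**What to change.** Add to section 7.2: after any single SAE rated possibly related or related on the 12.3 scale, by either the PI or Sub-PI or the TSC, no new patient receives a first dose until the TSC has reviewed the case. The review should be prompt and within a stated limit, for example 7 days. The TSC should record whether enrolment continues and whether dose or prophylaxis changes.

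Keep the two-patient rules, and leave patients already on treatment under 7.1.

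Restate the relatedness terms in 7.1 and 7.2 on the 12.3 scale. Section 12.3 records only unrelated, possibly related and related, so the probable and definite categories used in 7.1 and 7.2 match nothing on the form. The team must choose the mapping, because it sets the threshold for mandatory termination. Section 12.3 defines possibly related as unlikely to be due to other disease or drugs, so including it in the hold is not a loose trigger.

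The cost is a short addition to 7.2, some terminology edits, and a possible short delay for a later eculizumab-resistant patient, which the TSC can end once it has reviewed the case. The change adds a hold and a written record. It does not add independent oversight, since the minimum TSC is the same two people.

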#### 8.0 ACCOUNTABILITY PROCEDURES

The PI and the hospital pharmacist are responsible for study medication accountability, reconciliation, and record maintenance. Drug accountability records will be maintained during the study, including the amount of study medication received from the Sponsor, the amount distributed to each subject, and the amount of unused drug returned to the Sponsor or destroyed at Sponsors request. In addition, in the event of necessary disposal of opened but wasted medication, the disposal should be documented appropriately (ie, witnessed) in accordance with applicable local regulations, and "Good Clinical Practice" (GCP) procedures.

#### 9.0 SELECTION AND WITHDRAWAL OF SUBJECTS

Trialists will be patients with PNH and known genetically determined resistance to eculizumab who are willing to give informed consent to participate in the trial.

#### 9.1 Inclusion Criteria

- Males or females taking adequate contraceptive precautions if of childbearing potential, 18 80 years of age
- Body weight  $\geq$ 50kg and  $\leq$  100kg
- The patient has provided written informed consent.
- Willing to avoid prohibited medications for duration of study (see Exclusion Criteria)
- Must agree to take appropriate prophylactic precautions against Neisseria infection
- Must be counselled regarding the possible reproductive risks of using Coversin and be advised to use an adequate method of contraception pending further data on reproductive toxicology.

#### 9.2 Exclusion Criteria

- Body weight <50kg or >100kg
- Pregnancy

#### 10.0 NEISSERIA IMMUNISATION AND ANTIBIOTIC PROPHYLAXIS

It is known that the products of C5 complement activation are important in protection against infection by *Neisseria* species (15). This is believed to be the only known hazard of blocking this stage of the complement cascade and patients taking part in previous trials of complement C5 inhibitors were found to be at greater risk of *Neisseria* infection, particularly meningococcal infection (16). For this reason all patients entering the trial should where possible have received immunization against *Neisseria meningitidis* infection in the past, or must receive a booster shot of quadrivalent vaccine (against meningococci type ACW135Y) ) at the time of recruitment into the trial and at least prior to receiving the first dose of medication. In addition all patients should be immunised against Meningitis B using the *Bexsero*® vaccine as soon as this vaccine is available in the country where the patient is treated. This vaccine requires an initial dose followed by a booster 1 month later.

All patients will in addition have throat and nasal swabs taken after entry to the trial and prior to receiving the first dose. Cultures positive for any *Neisseria* species will not be grounds for excluding that subject from the trial but will alert the PI to use extra vigilance during and after induction of complement inhibition. Any patient having positive nasal swabs will be retested 7 days later to ensure that the pathogen has been eliminated by ciprofloxacin.

Patients will preferably receive a 5 day course of oral ciprofloxacin commencing the day before the first dose of Coversin and this will either be followed by oral penicillin prophylactic treatment or, at the discretion of the PI and in accordance with local custom, the patient may be provided with high dose ciprofloxacin to be started in the event of an actual or suspected infection. Patients will be instructed to make urgent contact with the PI or her deputy in that event.

Because of the known drug interaction between tizanidine and ciprofloxacin the former drug will be prohibited during this trial. In addition patients will be given a medication leaflet for ciprofloxacin in their native language in which other possible drug interactions (e.g. with antacids) and precautions regarding known or suspected sensitivity to fluoroquinolones will be pointed out. It is the responsibility of the PI and her deputies to make the patient(s) aware of these precautions.

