#### 3.0 TRIAL DESIGN

Treatment with Coversin comprises an ablating dose on day 1 and daily maintenance treatment from day 2 onwards. Calculated according to body weight, the ablating dose will be 0.57mg/kg. Thereafter the daily repeat maintenance dose will be titrated according to clinical response and complement inhibition as determined by CH50 ELISA. The initial daily maintenance dose will be 25% of the ablating dose (0.14 mg/kg) and this will be adjusted up or down if necessary once steady state is reached (5 days). This is further explained in chapter 6, TRIAL PROCEDURE .

In order to mitigate the risk of infection by *Neisseria sp* all subjects or patients taking part in the trial will be carefully instructed about precautions to be taken in case of actual or suspected infection. Patients may either be given permanent antibiotic prophylaxis (oral penicillin daily) or be provided with high dose ciprofloxacin and instructed to immediately commence taking it in the event of a suspected infection. In the latter case they will also be told to make immediate contact with the PI or her deputy. In addition all patients will receive immunisation with quadrivalent meningoccal vaccine Anti meningococcal B vaccine has recently been developed and will be given once approved in the country where the patient is treated. Vaccination against meningococci typ ACW135Y is required at the start of the study. Should the first vaccination take place  $\leq 14$  days of commencement of Coversin, then the patient must take high dose antibiotic for the first 2 weeks. This will generally be ciprofloxacin daily (2x 750mg orally, until 2 weeks have elapsed since first vaccination) or alternative antibiotic treatment directed against meningococci.

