#### 6.0 TRIAL PROCEDURE

The trial will comprise an open label, non-comparative study of minimally 1 patient and maximally 6 patients with PNH and known resistance to Eculizumab, who meet the inclusion and exclusion criteria (see below). Patients agreeing to participate in the trial will be admitted to the hospital for a minimum of 2 days for initiation of Coversin treatment, for clinical observation and for bloodsampling (PK/PD). Treatment will be continued on an out-patient basis with daily visits until stabilization or adjustment of dose.

Patients deemed capable of self-administration will be taught how to calculate and draw up the appropriate volume of solution for injection and how to inject subcutaneously. They will also be taught how to store and thaw Coversin prior to injection.

For Patients deemed not capable of self administration, alternative facilities for administration at home will be sought (General Physician or suitably qualified home care nurse).

Only if, in the opinion of the PI, the patient is capable of self injecting the correct dose of Coversin or adequate alternative facilities existfor safety monitoring and dosing supervision, treatment will be transferred to admisitration at home.

If not already immunised against *Neisseria sp.* immunisation and prophylactic antibiotics will be administered as set out in Section 10 below. Nose and throat swabs will be taken although growth of *Neisseria* species will not be grounds for exclusion but will prompt particular vigilance on the part of the PI.

The ablating dose will be divided between as many injection sites as are necessary to avoid injection of >1.2mL of Coversin solution for injection. These sites may be chosen from the deltoid regions, the anterior abdominal region or the anterior femoral regions. The injection sites used will be recorded in the patient notes and will be inspected at 24 hour intervals for 5 days for injection site reactions.

Doses of Coversin will be given at the same time each day, preferably between 6 and 8am. The time of each dose will be recorded in the CRFs. Patients self-administering Coversin will use suitable sites on the anterior femoral and anterior abdominal regions and the site, date and time of injection will be entered on the appropriate CRF sheet (patient diary) and be initialled by the supervising nurse.

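### Section 10, where Section 6.0 sends non-immunised patients for prophylaxis, omits Section 3.0's mandatory antibiotic rule after recent first vaccination

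*Combined protocol and SAP*

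**What the plan says.** Three sections of the protocol deal with antibiotics around the start of Coversin.

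- **Section 3.0 (Trial Design)** first gives every patient one of two options, daily oral penicillin or ciprofloxacin kept for use on suspicion of infection. It then adds a specific rule. If the first meningococcal vaccination falls 14 days or less from the start of Coversin, "then the patient must take high dose antibiotic for the first 2 weeks". The next sentence says that this will generally be ciprofloxacin 2 x 750 mg orally per day, "until 2 weeks have elapsed since first vaccination", "or alternative antibiotic treatment directed against meningococci".
- **Section 6.0 (Trial Procedure)** says that for patients not already immunised, "immunisation and prophylactic antibiotics will be administered as set out in Section 10 below". It does not mention Section 3.0.
- **Section 10.0 (Neisseria Immunisation and Antibiotic Prophylaxis)** allows the quadrivalent vaccine to be given "at the time of recruitment into the trial and at least prior to receiving the first dose of medication", so vaccination on the day of the first dose is permitted. On antibiotics it says: "Patients will preferably receive a 5 day course of oral ciprofloxacin commencing the day before the first dose of Coversin". No dose is given for that course. It is followed by oral penicillin or, at the PI's discretion and according to local custom, "the patient may be provided with high dose ciprofloxacin to be started in the event of an actual or suspected infection". The two-week rule does not appear, and nothing refers back to Section 3.0.

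**The concern.** The patients whom the Section 3.0 rule protects are those newly vaccinated around the start of treatment. Section 6.0 sends these same patients to Section 10, and Section 10 gives them a weaker default: a short course that is preferred rather than required, and then a choice that includes no continuous antibiotic at all. A site working from Section 10 could follow it exactly and still breach Section 3.0.

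Section 10 describes Neisseria infection as what is believed to be the only known hazard of blocking this stage of the complement cascade. By making the antibiotic mandatory, Section 3.0 treats recent vaccination alone as insufficient. At stake is a period of C5 blockade in a newly vaccinated patient without the cover that the protocol itself requires.

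**Working it through.** There is no sample size, power or error rate here. The check is a day count.

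**Inputs**

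- First Coversin dose on Day 1 (Section 3.0). The day before is labelled Day 0 in this count.
- First vaccination k days before the first dose, with k from 0 to 14 (the Section 3.0 trigger; k = 0 is allowed by Section 10).
- Required cover ends two weeks after first vaccination (Section 3.0).
- The Section 10 course is 5 days starting on Day 0, so it runs over Days 0 to 4. On Coversin it covers Days 1 to 4, which is 4 days.
- Assumption: the course counts as high-dose. Section 10 gives no dose, so this cannot be confirmed.
- Conditions for any gap: Section 10 is followed without Section 3.0, and reserve ciprofloxacin is chosen.

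**Formulas**

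- Coversin days on which cover is required: Days 1 to 14 − k, that is 14 − k days.
- Days without required cover after the course: max(0, (14 − k) − 4) = max(0, 10 − k).
- Days without required cover if the course is not given: 14 − k.

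| Vaccination, days before first dose (k) | Required Coversin days | Uncovered after 5-day course | Uncovered if course not given |
|---|---|---|---|
| 0 | 14 | 10 | 14 |
| 1 | 13 | 9 | 13 |
| 7 | 7 | 3 | 7 |
| 10 | 4 | 0 | 4 |
| 14 | 0 | 0 | 0 |

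The gap after the course shrinks by one day for each day of earlier vaccination and is nil from k = 10.

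**Check on the end point of the fix.** A rule ending exactly two weeks after vaccination would stop on Day 14 − k. For k = 11, 12, 13 and 14 that is Day 3, 2, 1 and 0, which is 1, 2, 3 and 4 days before the 5-day course ends on Day 4. The end should therefore be the later of Day 14 − k and Day 4.

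**The case against.** The strongest reply is that nothing is missing. Section 3.0 binds, Section 10 does not cancel it, and a site can comply with both, because a longer ciprofloxacin course contains the 5-day one. The PI's signature statement confirms that the site staff have read the whole protocol. Patients are admitted for at least 2 days and then have "daily visits until stabilization or adjustment of dose". Section 9.1 requires them to accept prophylactic precautions against Neisseria. Section 1.3 notes that patients on eculizumab are advised to keep their immunisation up to date, so few may need a first vaccination.

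Much of this stands, and it limits the point to an inconsistency of low severity. It does not remove it. Visits are supervision, not antibiotic cover. Section 6.0 expressly provides for patients who are not immunised, and it names only Section 10.

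Three stronger readings might be inferred, and the documents do not support them.

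- **That the protocol leaves newly vaccinated patients unprotected.** It does not, because the Section 3.0 rule remains in force.
- **That 14 uncovered days is the figure to expect.** This needs the preferred course to be skipped after same-day vaccination. Section 6.0 says that antibiotics will be given to these patients, which makes skipping less likely, although it defers to Section 10 for the details.
- **That the gap is 10 days for any vaccination in the window.** This takes the two-week phrase in Section 3.0 to mean the first two weeks of Coversin. The sentence that follows counts the two weeks from first vaccination, and the natural reading is that it defines the period.

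Choosing penicillin may also leave no gap, since Section 3.0 accepts an alternative antibiotic directed against meningococci. The documents do not say whether daily prophylactic penicillin qualifies.

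**Conclusion.** The inconsistency is real and should be corrected. A mandatory safety rule stands in the design section and is absent from the section to which the trial procedure directs the reader.

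Its size is at most 10 days on Coversin without the required cover after the 5-day course, for vaccination on the day of the first dose, falling to nil for vaccination 10 or more days before. The figure holds only if three things coincide: first vaccination inside the 14-day window, Section 10 followed without Section 3.0, and reserve ciprofloxacin chosen. It also assumes that the 5-day course is given and counts as high-dose.

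The number of patients affected is not given and could be anywhere from 0 to 6. With one supervised centre and Section 3.0 still binding, severity is low. The omission itself is plain on the text; how many patients it would expose is not known.

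**What to change.** 1. **Section 10.** Add that any patient first vaccinated 14 days or less before starting Coversin must take ciprofloxacin 2 x 750 mg orally per day, or another antibiotic active against meningococci, from the day before the first dose until the later of two weeks after first vaccination and the end of the 5-day course. The patient then moves to the usual long-term options.
2. **Section 3.0.** Replace the phrase about the first two weeks with the period counted from first vaccination, and give the same 5-day minimum, so that the two sections end at the same point.
3. **Section 6.0.** Cite both Section 3.0 and Section 10.

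The cost is protocol wording. Section 3.0 already requires the Coversin days up to two weeks after vaccination, so those are not new. The added burden is the pre-dose day and, for vaccination 11, 12, 13 or 14 days before the first dose, respectively 1, 2, 3 or 4 Coversin days of the 5-day course that become mandatory rather than preferred.
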